# 6.2.5 **Blinding**

The site pharmacy personnel who dispenses the study drug will not be blinded and will not be involved in any study assessments. All other participating staff involved in the evaluation and execution of the study will remain blinded to subject's study drug treatment.

### 6.2.6 **Unblinding the Treatment Assignment**

The treatment assignment must not be broken during the study except in emergency situations in which the identification of the investigational product is required for further treatment of the subject. The investigator should contact the medical monitor before unblinding, if possible. However, this should not delay unblinding in case of an emergency. The investigator should contact the medical monitor has been unblinded.

In the event that the treatment assignment is broken, the date, the signature of the person who broke the code, and the reason for breaking the code are recorded on the source documents. Upon breaking the blinding, the subject is withdrawn from the study, but should be followed up for safety purposes. Any code-breaks that occur must be reported to the Contract Research Organization (CRO) and sponsor.

# 6.3 Labeling, Packaging, Storage, and Handling

Further information regarding labeling, packaging, storage and handling can be found in the Pharmacy Manual.

## 6.3.1 Labeling

Each stock solution vial contains 88 mL of ganaxolone at a concentration of 3 mg/mL. A label is applied to each vial with information on strength, manufacturing batch number, manufacturing date, storage conditions, name of the manufacturer, and a warning that the drug is intended for research only.

The site pharmacy will prepare the IV bags, which will include at minimum the subject ID, protocol number, and time and date of IV bag preparation. No information which could potentially unblind the study drug should be visible to the subject or staff, and no packaging information should allude to the contents of the IV bag (e.g., "drug lot number"). Further details are provided in the pharmacy manual.

The Site Pharmacy will dispense the IV bag to a qualified blinded staff member who will administer the study drug to the subject.

For Cohort 6 the medication bottles (placebo and ganaxolone) will be labeled before shipping to the sites.

### 6.3.2 **Packaging**

### 6.3.2.1 IV ganaxolone

The sponsor will provide stock study drug solution which will be diluted by an unblinded research pharmacist at the investigative site. The sponsor will also provide or approve IV bags and empty syringes which are to be used for infusion and bolus dosing of the study drug and placebo. All packaging and labeling operations will be performed according to good manufacturing practice (GMP) and good clinical practice (GCP) guidelines. The study drugs will be prepared and supplied according to the randomization plan. Investigational products are prepared and distributed by the unblinded pharmacist. The pharmacist will enter the unique subject identifier on the investigational product as the product is distributed to the staff members managing administration of the study drug. Further details can be found in the pharmacy manual

6.3.2.2 Ganaxolone and placebo oral capsules

For Cohort 6 ganaxolone capsules and matching placebos will be provided in HDPE bottles.

All packaging and labeling operations will be performed according to good manufacturing practice (GMP) and good clinical practice (GCP) guidelines. Investigational products are prepared and distributed by the site pharmacist or delegated staff.

The site pharmacy or delegated site staff will be responsible for dispensing the study treatment to the subject. A sufficient number of capsules will be provided to the subject until the next study visit plus at least 3-day overage.

Detailed instructions when to take the medication and a reminder to take the study medication with fatty food (meal or snack, e.g., fatty yogurt, nuts, avocado) at dinner time and with 240 mL (8 oz) of water will be provided to the subject along with a medication diary to document intake of IP and fatty meal/snack  $\pm 15$  minutes.

# 6.3.3 Storage

The investigator has overall responsibility for ensuring that investigational product is stored in a secure, limited-access location. Limited responsibility may be delegated to the pharmacist, but this delegation must be documented.

The ganaxolone stock solution investigational product will be stored at refrigerated temperature 2°C to 8°C (36°F to 46°F).

The 0.3-micron ganaxolone capsules (225 mg) and matching placebos are stored in HDPE bottles with a foil induction seal and child resistant closure at room temperature ( $60^{\circ}$ F to  $75^{\circ}$ F).

Temperature monitoring is required at the storage location to ensure that the investigational product is maintained within an established temperature range. The investigator is responsible for ensuring that the temperature is monitored throughout the duration of the study and that records are maintained. The temperature should be monitored continuously through use of either an in-house system, a mechanical recording device such as a calibrated chart recorder, or by manual means, such that both minimum and maximum thermometric values over a specific time period can be recorded and retrieved as required. The sponsor or sponsor's delegate must be notified immediately upon discovery of any excursion from the established range. Temperature excursions will require site investigation as to cause and remediation. The sponsor will determine the ultimate impact of excursions on the investigational product and will provide supportive documentation as necessary. Under no circumstances should the product be dispensed to subjects until the impact has been determined and the product is deemed appropriate for use by the sponsor.

The sponsor or sponsor's delegate should be notified immediately if there are any changes to the storage area of the investigational product that could affect the integrity of the product(s), e.g. fumigation of a storage room.

# 6.4 Drug Accountability

Drug kits containing the study drug (ganaxolone stock vials for the IV solution, ganaxolone 225 mg capsules and matching placebo capsules) and supplies needed for each subject for the entire study will be supplied to the investigative site by the sponsor or a distributor on behalf of the sponsor. The pharmacist will inventory and acknowledge receipt of all shipments of the kits. The study drugs must be kept in a locked area with restricted access and stored and handled in accordance with the manufacturers' instructions. The pharmacist will also keep accurate records

of the quantities of study drug dispensed and used. The pharmacist is responsible for all drug supplies; written documentation is mandatory. The study monitor will periodically check the supplies of the study drug held by the pharmacist to verify accountability of all kits used. The pharmacist will dispense the kits according to the dosing plan. Upon receiving kits, the Principal Investigator and the team members will administer them only to the identified subjects in this study, following the procedures described in this study protocol and documented in the appropriate eCRF. At the conclusion of the study, all unused study drug will be returned or destroyed per the site's Standard Operating Procedures or instructions from the sponsor. The sponsor will verify that a final report of drug accountability to the unit-dose level is prepared and maintained in the Principal Investigator's study file.

# 6.5 Drug Administration

# 6.5.1 Administration of IV IP (Cohorts 1-6)

The IP will be administered IV via an indwelling catheter inserted in a vein on the arm or hand. The IP should be given as continuous infusion as instructed. If the study drug is stopped temporarily (e.g. catheter change) the infusion may be re-started at the same rate as before. A new infusion bag should be prepared every 24 hours. The catheter should be flushed with saline at the same time when the tubing is changed. The catheter site should be inspected for inflammation at least twice a day. For details please see pharmacy manual.

# 6.5.2 Administration of oral ganaxolone or placebo capsules (Cohort 6)

Oral doses of ganaxolone or matching placebo should be taken at dinner time with fatty food  $(\pm 15 \text{ minutes of a fatty meal or snack, e.g., fatty yogurt, nuts, avocado) and with 240 mL (8 oz) of water at home.$ 

Subjects participating in Cohort 6 will be informed about possible side effects from the study medication and cautioned to avoid quick postural changes. They should not carry the baby or sleep with the baby in the same bed due to the possible side-effect of dizziness and sedation. Subjects will be advised not to drive, operate heavy machinery, or participate in any potentially hazardous activity during the study that requires full mental alertness until they are sure the medication is not affecting alertness. They will also be cautioned that non-adherence to the dosing instructions (e.g. increasing the dose, taking the study medication doses too close together) could produce side effects.

The interaction between alcohol and ganaxolone is not known. Alcohol use is prohibited during the treatment period.

The subjects participating in Cohort 6 must have a reliable family member, significant other or a trusted friend who can take the role for being the primary childcare provider and a support person at home (including at nighttime) while the subject is participating in the trial.

# 7.0 STUDY PROCEDURES

This is a Phase 2A, double-blind, placebo-controlled, multiple-dose escalation study consisting of up to 6 cohorts. In Cohorts 1-5 the IV formulation of ganaxolone will be used while in Cohort 6 both IV and oral formulations will be used. Approximately 200 women with PPD 18 to 45 years of age will be screened to randomize approximately 100 subjects across the up to 6 cohorts. Approximately 10-30 subjects will be randomized into each cohort. Randomized subjects will receive ganaxolone or placebo in a 1:1 ratio. In Cohorts 1-5 the treatment is administered intravenously (with or without an initial bolus) over 60 hours. In Cohort 6 the treatment is initiated with a 6-hour intravenous (IV) infusion followed by oral ganaxolone or matching placebo. Additional subjects may be included into these cohorts or additional cohorts may be added, but will not exceed 100 randomized subjects for the study.

The screening period for each cohort will be up to 2 weeks. Following the screening period, there will be a 4-day inpatient treatment phase at a hospital or clinical pharmacology unit for Cohorts 1-5 during which a 60-hour infusion of ganaxolone or placebo will be administered (with or without bolus dosing). The subjects will be discharged from the unit on the morning of Day 4. There will be 2 safety follow-up visits after inpatient discharge on post-treatment Weeks 1 and 4.

[figure not shown]
In Cohort 6, following the screening period, there will be a 1-day inpatient treatment phase at a hospital or clinical pharmacology unit during which a 6-hour infusion of ganaxolone or matching placebo will be administered initially from 9 am to 3 pm ( $\pm$ 1 hour) before oral dosing is started at 7 pm ( $\pm$ 1 hour). The subjects will be admitted on Day 0 and discharged from the unit in the morning of Day 2. The first dose of oral ganaxolone (4 capsules; 900 mg) or matching placebo will be administered at dinner time (around 7 pm) of Day 1, 4 hours after the end of infusion on Day 1. Oral dosing is continued as outpatient on Days 2-28. The dosing regimen during the outpatient phase of Cohort 6 is 900 mg or placebo (4 capsules) at dinner time daily. A 3-day taper will follow at days 29, 30, and 31, as described in Section 3.4.6. There will be 3 safety follow-up visits after the last dose on post-treatment Weeks 1,4, and 6.

On Day 1 subjects will have 6 PK samplings: at 1 hour after the end of the 6-hour infusion (i.e., at 4 pm), at 7 pm (just prior to the oral dosing), and at 1, 2, 3, and 4 hours post oral dosing (at 8, 9, 10, and 11 pm) as well at 8 am the following morning (on Day 2) prior to discharge.

The subjects will take a 900 mg dose or placebo (4 caps) on the evening of Day 1 at dinner time and continue with the 900 mg dose or matching placebo at dinner time on Days 2-28. A 3-day taper will follow as described in Section 3.4.6.

A schematic of the study design if provided in Figure 1.

### Figure 1: Study Design Flow Chart

## 7.1 Screening Visit and Screening Period (day -14 to -1) – Cohorts 1-6

- Obtain written informed consent
- Collect demographics, medical history, review prior medications, review of concomitant medications and therapies,
- Assess CGI-S
- Conduct MINI international neuropsychiatric interview
- Conduct Hamilton Depression Rating Scale 17-item version (HAMD17) interview
- Edinburgh Postnatal Depression Scale (EPDS)
- Spielberger State-Trait Anxiety Inventory (STAI6)
- Perform a physical examination
- Collect vital signs (BP, pulse, temperature, pulse oximetry, respiratory rate)
- Collect ECG
- Collect urine sample for urinalysis, drug screen and urine pregnancy test
- Collect safety laboratory tests
- Measure height and weight
- Conduct CSSRS interview
- Review inclusion and exclusion criteria. Screen failure is defined as a subject who has given informed consent, and failed to meet the inclusion criteria and/or met the exclusion criteria
- Schedule a SAFER interview if the subject meets the eligibility criteria. The SAFER interview will be conducted during the screening period. The investigative site must wait for the results of the SAFER interview before admitting the subject on the unit.

- Screening period may be extended to 21 days with approval from the medical monitor (e.g. a laboratory sample was hemolysed which had to be repeated causing a delay).
- The subject may stay on the inpatient unit voluntarily between screening visit and admission to the study (Day 0) provided that close monitoring of the subject can be ensured. The gap between the screening visit and admission (Day 0) should be kept as short as possible, preferably no more than 2 days. Q15 minute health checks should be implemented during the gap period. The SAFER interview will be done during the gap period. The sponsor should be informed of this decision.

# 7.2 Admission to the Unit (Day 0) – Cohorts 1-6

- Review concomitant medications and therapies
- Admission to the unit. The subject arrives on the unit the day before the start of the infusion (Day 1) to complete assessments and accommodate to the unit.
- Collect vital signs (BP, pulse, temperature, pulse oximetry, respiratory rate)
- Collect ECG
- Collect urine sample for urinalysis, drug screen and urine pregnancy test
- Collect safety laboratory tests
- Collect neurosteroid level
- Measure weight
- CTNI to conduct HAMD17 interview
- Collect AEs
- Conduct CSSRS interview
- Review inclusion and exclusion criteria (including hematology and chemistry from the screening visit); HAMD17 (conducted by CTNI) must be ≥ 22 for randomization.
- Start Q15 minutes health checks (e.g. to observe general wellbeing and behavior, monitor infusion)
- If the subject is breastfeeding, she is encouraged to "pump and dump" while inpatient and for 45 days after the discharged from the unit. She should be provided with a breast pump.

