#### 3.4.5 **Cohort 6**

For Cohort 6, the goal of initiation of treatment with IV infusion followed by oral capsules is to maximize the speed of onset of antidepressant activity while providing the convenience of oral dosing for the remainder of the treatment period. Under this IV-oral dosing schedule there may not be a need for a prolonged inpatient observation.

This initial infusion is targeted to provide a fast onset of antidepressant activity by delivery of rapid plasma exposures to ganaxolone. At dinner time of Day 1 the subjects will take their first oral dose of ganaxolone 900 mg or matching placebo (4 capsules). This dose is expected to provide mean  $C_{max}$  plasma concentrations of approximately 250-300 ng/mL and mean steady-state levels between 90 and 150 ng/mL, which may be mildly sedating. In previous studies ganaxolone has been given up to a daily dose of 2000 mg, and at single doses of 1000 mg. Based on the previous experience this dose is expected to be safe.

At subsequent nights (Days 2-28), the target dose is ganaxolone 900 mg or matching placebo (4 capsules) at dinner time followed by a 3-day taper (3, 2, and 1 capsule/s per day, respectively). However, based on the assessment of the investigator the dose may be maintained at 675 mg or 450 mg (or matching placebo) in case of adverse events, such as grogginess in the morning. In the case of 3 capsules per day on day 28 the taper will consist of 2, 2, and 1 capsule/s on days 29, 30, and 31, respectively. In the case of 2 capsules per day on day 28 the taper will consist of 1 capsule on days 29, 30, and 31. If the subject cannot tolerate 450 mg (or matching placebo) per dose the investigator will contact the Medical Monitor to discuss dosing options.

Subjects will be provided with a diary to capture the details of dose administration and associated food intake throughout the treatment period. Subjects will document the number of capsules taken and whether a fatty meal/snack (e.g., fatty yogurt, nuts, avocado) was consumed  $\pm 15$  minutes of taking the capsules.

The mechanism by which ganaxolone is postulated to be efficacious under this dosing regimen is restructuring of sleep architecture. Preclinical studies have shown that allopregnanolone has the capacity to modulate sleep, and disturbed sleep architecture is one of the hallmarks of depression.

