#### 3.6 Study Duration

The screening period for each cohort will be up to 2 weeks. In Cohorts 1-5 the screening period is followed by a 60-hour infusion treatment with or without initial bolus dosing during the 4-day inpatient treatment phase at a hospital or clinical pharmacology unit. The subjects will be discharged from the unit on the morning of Day-4. There will be 2 safety follow-up visits after inpatient discharge on post-treatment Weeks 1 and 4. The total duration of the study will be up to 7 weeks for Cohorts 1-5. For Cohort 6 there will be an initial infusion treatment and oral dose during the approximately 24-hour inpatient dosing phase followed by 27 days of oral treatment as outpatient. There will be 3 safety follow-up visits after the outpatient treatment period on post-treatment Weeks 1,4, and 6. The total duration of the study will be up to 12 weeks for subjects participating in Cohort 6.

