#### 4.1 Inclusion Criteria

The subject will not be considered eligible for the study without meeting all of the criteria below.

- 1. An understanding of and ability, and willingness to fully comply with study procedures and restrictions.
- 2. Ability to voluntarily provide written, signed, and dated informed consent as applicable to participate in the study.
- 3. Female aged 18 to 45 years, inclusive, at the Screening Visit
- 4. Experiencing a Major Depressive Episode, which started between the start of the third trimester and 4 weeks following delivery. The Major Depressive Episode must be diagnosed according to MINI 7.0 interview
- 5. Given birth in the last 12 months
- 6. HAMD17 score of  $\geq$  26 at screening (HAMD17 must be  $\geq$  22 per CTNI rating at Admission to the Unit on Day 0)
- 7. The diagnosis of PPD and severity of depression must be supported by the SAFER interview
- 8. Must agree to stop breastfeeding from start of study treatment to 45 days after end of study treatment
- 9. Must agree to use acceptable contraceptive methods during the study period

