#### 4.4 Discontinuation of Subjects

A subject may withdraw from the study at any time for any reason without prejudice to their future medical care by the physician or at the institution. The investigator or sponsor may withdraw the subject at any time (e.g. in the interest of subject safety). The investigator is encouraged to discuss withdrawal of a subject from the investigational product with the medical monitor when possible. Withdrawn subjects who have not received IP will be replaced.

If the investigational product is discontinued, regardless of the reason, the evaluations listed for Day 4 are to be performed as completely as possible for Cohort 1-5, and Day 28 evaluations for Cohort 6. Whenever possible, all discontinued subjects should also undergo the protocol-specified follow-up. Comments (spontaneous or elicited), complaints or AEs reported by the subject must be recorded in the source documents. The reason for discontinuation and the date and time of discontinuation of the investigational product must be recorded in the case report form (eCRF) and source documents.

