## 7.6.7 Visit 8 (Day +29 ±3 days)

• CTNI to conduct HAMD17 interview

- EPDS
- STAI6
- Assess CGI-I
- Review concomitant medications and therapies
- Collect vital signs (BP, pulse, temperature, pulse oximetry, respiratory rate),
- Collect ECG
- Collect urine sample for urinalysis, drug screen and urine pregnancy test
- Collect safety laboratory tests
- Collect a pharmacokinetic sample
- Measure weight
- Stanford Sleepiness Scale (SSS)
- Conduct CSSRS interview
- Collect AEs
- Dispense study medication with a supply to last through the taper period. Provide the subject with dosing instructions. IP return and accountability.
- Begin 3-day taper (3 capsules on Day 29, 2 capsules on Day30, 1 capsule on Day31, or, if Day 28 dose is other than ganaxolone 900 mg or placebo, follow instructions in section 3.4.6)
- Perform physical examination

# 7.7 Post-treatment Follow-up Period (Days +29 to +71) – Cohort 6

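### Protocol 7.2 counts the 45-day pump-and-dump period from discharge, which in Cohort 6 ends on Day 47, 29 days before the Day 76 that inclusion criterion 8 implies

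*Protocol*

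**What the plan says.** Two current passages of the protocol set a duration for the same measure.

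- **Inclusion criterion 8** (Protocol 4.1, repeated in the synopsis): "Must agree to stop breastfeeding from start of study treatment to 45 days after end of study treatment". The clock starts at the end of treatment.
- **Protocol 7.2**, the Day 0 admission procedures for Cohorts 1-6: a breastfeeding subject is encouraged to pump and discard her milk "while inpatient and for 45 days after the discharged from the unit", and is to be given a breast pump. The clock starts at discharge.

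The heading of Protocol 7.5 sends Cohort 6 to 7.2 for its admission visit, and sections 7.5 to 7.7 give no separate Cohort 6 rule.

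The Cohort 6 calendar is in Protocol 7.0: "The subjects will be admitted on Day 0 and discharged from the unit in the morning of Day 2". Oral dosing then runs at home through Day 28, and "A 3-day taper will follow at days 29, 30, and 31". The taper after a reduced dose of three capsules also ends on Day 31 (Protocol 3.4.5: "the taper will consist of 2, 2, and 1 capsule/s on days 29, 30, and 31, respectively"), as does the taper from two capsules.

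The protocol does not define the end of study treatment. The 7.7 heading, "Post-treatment Follow-up Period (Days +29 to +71", starts the post-treatment period before the taper is finished. Section 3.6 describes the Cohort 6 inpatient phase as "followed by 27 days of oral treatment as outpatient", which leaves the taper out of the count.

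**The concern.** When discharge and the last dose fall within a day of each other, it hardly matters which one starts the clock. That is the situation in Cohorts 1-5. Cohort 6 separates the two by about a month: the mother goes home on Day 2 and continues taking capsules.

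Section 7.2 is the only procedural text that tells staff how long the precaution lasts. The home-dosing cautions in Protocol 6.5.2 deal with carrying the baby, bed sharing, driving and alcohol, not breastfeeding. Staff who take the end date from the admission checklist would therefore arrive at a date well before the one the subject agreed to at enrolment. What is at stake is a consistent instruction on a precaution for the infant. No endpoint or analysis is affected.

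**Working it through.** **Day-count convention.** The protocol's own follow-up days are reproduced by adding the interval to the anchor day:

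- Cohort 6: 29 + 7 = 36, 29 + 28 = 57, 29 + 42 = 71, as stated in 7.7.1 to 7.7.3.
- Cohorts 1-5: 4 + 7 = 11, 4 + 30 = 34, as stated in 7.4.1 and 7.4.2.

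The same rule, end day = anchor day + 45, is used below.

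**Inputs.**

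- Cohorts 1-5: infusion ends at +60h on Day 3; discharge at +72h on Day 4 (7.3.2 and Table 1).
- Cohort 6: discharge on Day 2, last full dose on Day 28, last taper dose on Day 31 (7.0, 3.4.5).

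**End dates.**

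| Case | Protocol 7.2 | Criterion 8 | Criterion 8 minus 7.2 |
|---|---|---|---|
| Cohorts 1-5 | 4 + 45 = Day 49 | 3 + 45 = Day 48 | -1 day |
| Cohort 6, taper counted | 2 + 45 = Day 47 | 31 + 45 = Day 76 | 29 days |
| Cohort 6, taper not counted | 2 + 45 = Day 47 | 28 + 45 = Day 73 | 26 days |

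**Part of the 45 days left under 7.2 in Cohort 6.**

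- From the last taper dose: 47 - 31 = 16 days; 16/45 = 36%.
- From the last full dose: 47 - 28 = 19 days; 19/45 = 42%.

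**Effect of the visit window.** Visit 8, where taper supply is dispensed and the taper starts, is scheduled for Day 29 ±3 days (7.6.7). If the taper moves with the visit (an assumption, since 3.4.5 and 7.0 name fixed days), it starts between Day 26 and Day 32 and its last dose falls between Day 28 and Day 34. Criterion 8 then ends between 28 + 45 = Day 73 and 34 + 45 = Day 79, and the gap is 26 to 32 days.

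**Early stopping.** Protocol 4.4 sets evaluations "If the investigational product is discontinued, regardless of the reason" but does not mention the breastfeeding period. For a last dose on Day d, assuming discharge on Day 2 and no taper, the gap is (d + 45) - 47 = d - 2. That is 6 days for d = 8, 13 for d = 15 and 20 for d = 22.

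**The case against.** The strongest reply is that the governing rule is already right. Criterion 8 stands in both the synopsis and 4.1, and 7.2 itself lists a review of the inclusion and exclusion criteria on the same day, so staff carrying out 7.2 have criterion 8 in front of them. The investigator must follow the whole protocol, not one bullet. Breastfeeding status is also part of the physical examination (7.8.5), which in Cohort 6 is done before discharge and on Days 15 and 29. Most of this stands. It is why the point is minor, and why the text supports saying only that a site could give the wrong date, not that it would.

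These safeguards do not remove the conflict. The examination sets no end date and its last occurrence is Day 29. The Day 57 and Day 71 visits fall between the two end dates, and 7.7.2 and 7.7.3 list no physical examination. The Day 76 end date comes after the last scheduled visit, so the mother depends on having been given the right date earlier.

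Two stronger readings are tempting, and the documents support neither.

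- A reader might infer that the protocol allows Cohort 6 mothers to breastfeed from Day 47. It does not: 7.2 encourages discarding milk and is silent on resuming, while criterion 8 requires abstaining for longer.
- A reader might infer that infants will be exposed to ganaxolone. The documents give no figure from which exposure at Day 47 could be computed. The consent pages are not available here, so what mothers are told there is unknown.

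**Conclusion.** The inconsistency is real and confined to Cohort 6. Two current instructions give end dates 29 days apart, Day 47 and Day 76, with the taper counted as study treatment. That is the better reading, because the taper capsules are investigational product. If treatment is taken to end on Day 28, the gap is 26 days; if the taper follows the Visit 8 window, it is 26 to 32 days. In Cohorts 1-5 section 7.2 is one day longer than criterion 8, so there is no shortfall.

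The result rests on discharge on Day 2 and on the protocol's own day counting. It shows a conflicting site instruction under which a Cohort 6 mother could receive an end date 16 days after her last dose instead of 45. It shows neither a permission to breastfeed nor harm to an infant. Severity is minor.

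**What to change.** Reword the 7.2 bullet so that the period runs *while the subject is an inpatient and until 45 days after her last dose of study treatment, counting the taper or, if treatment stops early, the last dose actually taken*. This covers all six cohorts, settles whether the taper counts, and gives early stoppers a rule.

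Have the site repeat the resulting end date to the subject at the Day 2 and Day 29 visits in Cohort 6, and update it if the last dose changes.

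The cost is one corrected line in a protocol amendment and a reminder at two visits that already take place. No new visits, data or subjects are needed, and the SAP is unaffected.
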